## 2: Specific Aims

Aim 1: Determine whether cellular substrates of differential hormone sensitivity can be identified through creating neuronal progenitors exposed to high dose estradiol (E) and progesterone (P) (100nm each x 3 days) and withdrawal (3 days), with transcriptomic analyses conducted after each treatment.

Aim 2: a) Determine whether transcriptional response in immune-relevant pathways to hormone response and withdrawal in LCLs will, in these long term cultured cells, distinguish women with PPD from controls and, therefore, further implicate differential immune responses in the pathophysiology of PPD; and b) replicate differences in the polycomb repressor complex under both basal and E- and P-stimulated conditions that we previously observed in premenstrual dysphoric disorder (PMDD).

Hypotheses: H1) After exposure to combined E and P, neural progenitor cells from women with PPD will reveal a transcriptional pattern that differs from that in controls; H2) Similar to PMDD, LCLs from women with PPD will demonstrate a differential basal and hormone-stimulated transcriptional response in network and pathways analyses(e.g., Weighted Genome Correlation Network Analysis (WGCNA), Gene Set Enrichment Analysis (GSEA), and Database for Annotation, Visualization and Integrated Discovery (DAVID)).

Experimental Plan: This component of our protocol will build on access to unique samples of women with peripartum mood disorders as follows: 1) to create human-induced pluripotent cells (h-iPSCs) and neuronal progenitor cells whose transcriptional responses to ovarian steroids in vitro will be assessed; and 2) to create lymphoblastoid cell lines (LCLs).

Participants: PPD- Peripheral blood samples will be obtained from women with PPD and control women (matched for age, race and parity) who met the following criteria: 1) participated in the GnRH agonist and E/P replacement-then-withdrawal paradigms conducted at the NIMH IRP; and 2) clearly demonstrated recurrence of depression (in the women with past PPD but not controls) after E/P withdrawal. This group of women with past PPD and controls therefore will represent a highly selected phenotype in which we have demonstrated behavioral ovarian steroid

sensitivity (in past PPD) or the absence of this phenotype (in controls). All women will be otherwise healthy, and medication free.

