Analysis of RNA sequencing data: Reads will be mapped to reference genome Hg19 and normalized. Using edgeR analyses (or other similar platforms), performed in either CLC Bio Workbench 11 or “R” programming environment (or other appropriate environment), differentially expressed genes will be computed between conditions and multiple comparisons will be corrected using the False Discovery Rate (FDR, Benjamini Hochberg) method. For each gene of interest, normalized expression between untreated and hormone treated/withdrawn cell cultures will be further analyzed by 2-way ANOVAs, with hormone condition (i.e., untreated, hormone exposure, hormone withdrawal) as the within-groups factor and diagnostic group (i.e., PPP or PPD versus Controls) as the between-groups factor. The appropriate post-hoc tests will be performed should significant interactions be detected.

Pathway/Network analysis of RNA sequencing data: Pathway/Network analyses (e.g., Gene Set Enrichment Analysis (GSEA)) will be performed on differentially expressed genes to identify significant biological processes, molecular functions and cellular components for samples in the baseline (untreated), E/P-treated condition, and after withdrawal. Additional analyses that could be performed include WGCNA to examine modules of differentially expressed genes between cells from women with PPD and controls under each hormone condition. Finally, we will subject all differentially expressed genes to other bioinformatics tools, such as the Database for Annotation, Visualization and Integrated Discovery (DAVID) to identify functionally related groups and networks, which can help to detect impacted biological, molecular and cellular functional domains.

Validation of RNA-sequencing: mRNA expression analysis using qRT-PCR will be used to quantitate differentially expressed genes at baseline, after E/P exposure, and after E/P withdrawal. TaqMan qRT-PCR assays will be carried out according to the assay developer’s

recommended conditions on a 7900HT Fast Real-Time PCR System. A two-tailed, unpaired Students t-test will be performed for each comparison.

Additional Analyses: it is possible that whole exome sequencing will be performed in these samples, and evaluations of the methylome will be performed on repeated DNA samples across each of the hormonal conditions established in the clinical protocol (i.e., baseline, add-back, withdrawal and follow-up).

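### GSEA is planned on differentially expressed genes only, which discards the ranking it needs and leaves H2 and Aim 2a to over-representation of a filtered list, blind to modest pathway shifts

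*Combined protocol and SAP*

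**What the plan says.** The relevant text is in the combined protocol and SAP, Section 1 (Introduction), under 2: Specific Aims.

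- **Gene selection** (Analysis of RNA sequencing data): "differentially expressed genes will be computed between conditions and multiple comparisons will be corrected using the False Discovery Rate (FDR, Benjamini Hochberg) method". The method is edgeR or similar. No false discovery rate cut-off or fold-change rule is stated.
- **Pathway step** (Pathway/Network analysis of RNA sequencing data): these analyses, with GSEA as the named example, "will be performed on differentially expressed genes to identify significant biological processes, molecular functions and cellular components". The samples are those at baseline, under hormone treatment and after withdrawal.
- **WGCNA**, as an option: "Additional analyses that could be performed include WGCNA to examine modules of differentially expressed genes between cells from women with PPD and controls".
- **DAVID** is to receive all the differentially expressed genes.
- **Hypothesis H2**: "LCLs from women with PPD will demonstrate a differential basal and hormone-stimulated transcriptional response in network and pathways analyses", with WGCNA, GSEA and DAVID as examples. Aim 2a likewise asks about immune-relevant pathways.

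No section provides for GSEA on the full ranked list of measured genes.

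**The concern.** GSEA and over-representation need different inputs. Over-representation, as in DAVID, starts from a selected list and asks whether a set's members are too common in it. GSEA starts from every measured gene, ranked, and asks whether a set's members sit towards one end. If the list is cut to significant genes first, the members that moved but missed the cut-off are gone, and so are the unaffected genes that serve as the comparison. What remains compares significant genes with other significant genes.

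H2 is to be judged through network and pathway analyses, so this step is its test. As written, the one method on the list that can pick up a modest shift spread over a pathway is given an input that removes that ability. A null pathway result could then reflect the filter rather than the biology.

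**Working it through.** **Inputs.** The documents give no number of cell lines, cut-off, gene-set size or power for this component, so there is no planned figure to reproduce. The four groups of ten in Section 10 size the clinical repeated-measures analysis. Every setting below is an assumption.

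Main setting: 12,000 independent genes; 10 lines per group, PPD versus control, unpaired; one 50-gene set with every gene shifted 0.5 SD the same way; 200 unrelated genes shifted 2 SD; per-gene t-tests; Benjamini-Hochberg at 5%; set tested at 0.05/100 = 0.0005.

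**Step 1: how many set genes survive.** Let R be the expected number of genes called and a the per-gene cut-off, so a = 0.05 × R / 12,000. Let π(d) be the chance that a noncentral t (18 df, noncentrality d × √(10/2)) passes the cut-off. Then R = 200 π(2) + 50 π(0.5) + 11,750 a.

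- Solution: R ≈ 128, a = 0.05 × 128 / 12,000 = 0.00053, critical |t| = 4.20.
- Check: 200 × 0.607 + 50 × 0.0060 + 11,750 × 0.00053 ≈ 121.5 + 0.3 + 6.3 = 128.
- Set genes: noncentrality 0.5 × √5 = 1.12, π = 0.0060, so 50 × 0.0060 = 0.30 survive. Simulation gave 0.27.

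**Step 2: over-representation of the selected list.** With 128 of 12,000 genes called, the hypergeometric tail for a 50-gene set is about 0.002 for four or more members and about 0.0002 for five or more. Five are therefore needed at 0.0005. With a mean of 0.30, the Poisson chance of five or more is about 2 in 100,000. Simulation: 0% detection.

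**Step 3: other settings.** A second simulation used 15,000 genes, 0 or 200 unrelated shifted genes (200 in the last two rows), and a set threshold of 0.05/1000.

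| Lines per group | Shift (SD) | FDR | Set genes kept of 50 | Over-representation | Ranking within selected list |
|---|---|---|---|---|---|
| 5 | 0.4 to 0.6 | 5% | 0.00 | 0% | 0% |
| 10 | 0.4 to 0.6 | 5% | 0.00 to 0.36 | 0% | 0% |
| 20 | 0.4 to 0.6 | 5% | 0.01 to 2.51 | 0% | 0% |
| 10 | 0.6 | 10% | 0.81 | 0% | 0% |
| 20 | 1.0 | 5% | 16.6 | 100% | 0% |

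The last row separates the two methods. With a large shift, over-representation works, while ranking within the selected list still fails. In the 12,000-gene setting, over-representation found a 1.5 SD shift in about 99% of runs with 10 lines per group. It found a 1.0 SD shift in about 20% with 10 and 100% with 20.

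**Step 4: what the full list would give.** A gene-level rank test on the full list detects the 0.5 SD set in 100% of runs, but only if genes are independent. With within-set correlation ρ, the variance of the set's mean statistic is inflated by 1 + 49ρ.

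- ρ = 0.1: inflation 5.9. The critical z of 3.48 for p < 0.0005 acts like 3.48 / √5.9 = 1.43, so with no true shift the test rejects about 15% of the time.
- ρ = 0.3: inflation 15.7, 3.48 / √15.7 = 0.88, about 38%.

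Simulation gave 15% and 37%, against a nominal 0.05%. Correcting for the inflation, a rough normal approximation to power for the 0.5 SD shift is:

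- ρ = 0.1: 1.118 / √(5.9/50) = 3.25; Φ(3.25 − 3.48) ≈ 41%.
- ρ = 0.3: 1.118 / √(15.7/50) = 2.00; Φ(2.00 − 3.48) ≈ 7%.

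A sample-permutation set test at the looser p < 0.005 detected the set in 81% (ρ = 0.05) and 40% (ρ = 0.10) of runs with 10 lines per group, and in 100% and 93% with 20. The normal approximation is therefore on the generous side. With the same correlations, over-representation after filtering (p < 0.0005) found the set in 0% of runs with 10 lines and 2% to 4% with 20. The thresholds differ, so this comparison shows direction only.

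**The case against.** The strongest reply is that H2 still has a valid test. It names its tools as examples, DAVID is one of them, and a selected list is DAVID's proper input. That stands: large pathway shifts would be found.

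A reader might infer that H2 concerns small coordinated shifts, so that the filter removes exactly what it predicts. H2 says no such thing. It predicts a different response in network and pathway analyses, of unstated size. A reader might also infer that any real pathway difference would be missed, or that a full-list analysis would detect it with certainty. Step 3 contradicts the first. Step 4 contradicts the second, because the 100% figure needs independent genes and the test behind it is invalid without them.

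Other points stand in part:

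- WGCNA is optional, and its wording does not say that networks are built from the selected genes alone. It needs clarifying rather than correcting.
- The gene-selection text does not say which conditions are compared. Paired hormone contrasts within a line could have more power than the unpaired contrast used here.
- That donors will be few is an assumption. The Participants paragraph restricts them to women who completed the paradigm with the expected response, but gives no number.
- This is a laboratory component on opportunistically collected blood, separate from the randomised mood comparison.

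None of this makes a selected list the right input for GSEA.

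**Conclusion.** The point holds for GSEA. The plan states the input as a rule, and followed literally it makes GSEA uninformative and leaves H2 and Aim 2a to over-representation. Under the assumed settings, shifts of 0.4 to 0.6 SD leave on average between 0 and about 2.5 of 50 set genes with 5 to 20 lines per group, and over-representation detected none of them. Shifts of 1.0 SD with 20 lines, or 1.5 SD with 10, are found almost always.

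The direction is consistent across both sets of assumptions. The percentages are illustrations, not trial figures. How much a full-list analysis would gain depends on within-set correlation and cannot be read from the documents. This is a worthwhile correction to a secondary laboratory analysis; it has no bearing on the analysis in Section 10.

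**What to change.** Amend the pathway/network paragraph as follows.

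1. Run GSEA on all expressed genes, ranked by the edgeR statistic for each named contrast: PPD versus control, and diagnosis by hormone condition.
2. Use sample permutation or a correlation-adjusted set test, not one that treats genes as independent. Permute diagnosis across donors, keeping each donor's hormone conditions together. With 5 lines per group there are only 252 label arrangements (10 choose 5), so the correlation-adjusted test would then be preferable.
3. If WGCNA is done, build modules from all expressed genes, then test them against diagnosis and hormone condition.
4. Keep DAVID on the FDR-selected list, with expressed genes as background, and state the cut-off and the contrast that define the list.

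The cost is a change of wording and somewhat more analysis work. Sequencing is already whole-transcriptome, so no further samples, data or participant burden are needed. The second item is essential: full-list GSEA without it could replace missed pathways with false ones.

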h-iPSCs: h-iPSCs will be generated from Sendai virus-transformed T cells (74), a procedure already successfully accomplished in the LNG laboratory, and then differentiated to neuroprogenitor cells (75) (also successfully achieved by LNG), serotonergic (76) (experiments underway in LNG) and dopaminergic neurons (77), (69). Following differentiation, cells will be cultured in a sex steroid-free growth medium which is phenol red-free media to reduce possible exposure to steroid-like activity prior to experimental exposure.

LCLs: EBV-transformed lymphoblastoid cell lines will be made from peripheral blood as described previously (78), and cells from women with PPD and matched controls will be cultured under identical conditions. As for IPSCs, 5 days before hormone exposure, LCLs will be cultured in a sex steroid-free growth medium of phenol red-free media supplemented with 15% knock out serum (KOSR) (estrogen-depleted).

PPD and control cells will be cultured and collected at baseline, after exposure to combined E/P at supraphysiologic doses of 100nm each (in DMSO) for 3 days, and after withdrawal to vehicle only (DMSO alone) or continued E/P treatment for 3 days (to control for latency following initial hormone exposure).

RNA sequencing: Total RNA will be isolated from the cell pellets and then treated with DNase to remove any traces of genomic DNA contamination. Quality assessment of the RNA is done by an Agilent® 2100 Bioanalyzer. Whole-transcriptome RNA sequencing will be performed using an Ion Torrent NGS Sequencer, the Ion Proton. Total RNA will be polyAAA selected and used to prepare cDNA libraries using the Ion Total RNA-Seq Kit v2, barcoded with Ion Xpress™ RNA-Seq Barcodes.

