**10. Statistical Analysis:**

Analysis of Data: A repeated measures design has four groups of ten subjects each for a total of forty subjects. Each subject is measured during the hypogonadal baseline, at the end of the two months of addback, and during the following month (i.e., continued addback in group 2 or withdrawal in group 1). The effect of hormonal addback and withdrawal in subjects and controls on mood and biological parameters will be calculated using ANOVA-R with post-hoc Bonferroni t-tests.

Sample Size Justification: Based on previous data (61), the between-subject standard deviation is 0.69 and the within-subject standard deviation is 0.28. This design achieves 67% power when an F test is used to test the Groups factor at a 5% significance level and the actual standard deviation among the appropriate means is 0.30 (an effect size of 0.43), achieves 81% power when an F test is used to test the Times factor at a 5% significance level and the actual standard deviation among the appropriate means is 0.16 (an effect size of 0.57), and achieves 60% power when an F test is used to test the group by time interaction at a 5% significance level and the actual standard deviation among the appropriate means is 0.13 (an effect size of 0.46).

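### The qRT-PCR validation names an unpaired t-test although hormone conditions are repeated on the same cell lines; for contrasts between conditions within a line this is conservative and can lose substantial power

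*Combined protocol and SAP*

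**What the plan says.** All of this is in the combined protocol and SAP, section 1 (Introduction), subsection 2: Specific Aims.

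- **Cell culture (LCLs paragraphs).** "PPD and control cells will be cultured and collected at baseline, after exposure to combined E/P", and again after three further days of either vehicle or continued hormone. Each woman's line therefore contributes to several conditions.
- **Analysis of RNA sequencing data.** Genes of interest go into a two-way ANOVA "with hormone condition (i.e., untreated, hormone exposure, hormone withdrawal) as the within-groups factor"; diagnosis is the factor between groups.
- **Validation of RNA-sequencing.** qRT-PCR "will be used to quantitate differentially expressed genes at baseline, after E/P exposure, and after E/P withdrawal". The only test named for these data is: "A two-tailed, unpaired Students t-test will be performed for each comparison".

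The validation paragraph does not list the comparisons. It gives no number of lines, effect size, within-line correlation, alpha or power.

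**The concern.** The plan treats hormone condition as repeated within a line when it analyses the sequencing data. When it validates the same genes at the same conditions by qRT-PCR, it names a test for independent samples. Read literally, each comparison includes baseline against E/P and E/P against withdrawal, and these are differences within a line.

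Stable differences between women's lines cancel from a paired difference but stay in the unpaired standard error. A real hormone effect is then harder to show in the validation assay than the data would allow. Hormone response and withdrawal are the subject of Aims 1 and 2a, so these contrasts are natural targets for validation.

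**Working it through.** **Inputs from the documents.** Three conditions measured on the same lines; hormone condition a within factor; diagnosis a between factor; two-tailed unpaired t-test. The plan states no power figure for this step, so there is none to reproduce.

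**Assumptions.** Two-sided alpha 0.05; n lines in the contrast; equal SD in each condition, set to 1; correlation rho between two conditions on the same line; normal data; d the hormone effect in SD units.

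**Step 1, standard errors.**
- The true variance of the mean difference is 2(1 - rho)/n.
- The unpaired test estimates it as 2/n.
- The unpaired SE is therefore too large by 1/sqrt(1 - rho): 1.12 at rho 0.2, 1.41 at 0.5, 1.83 at 0.7, 2.58 at 0.85.

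**Step 2, power with n = 10 and d = 0.8.** Paired power is exact: noncentral t with n - 1 = 9 df and noncentrality d x sqrt(n/(2(1 - rho))). At rho 0.5 this is 0.8 x sqrt(10/1) = 2.53, which gives 62%. Unpaired power on the same correlated data comes from simulation (400,000 data sets per cell, 18 df). Type I error is simulated in the same way with d = 0.

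| rho | Unpaired power | Paired power | Type I error, unpaired |
|---|---|---|---|
| 0 | 40% | 36% | 5.0% |
| 0.2 | 39% | 43% | 3.1% |
| 0.3 | 38% | 48% | 2.2% |
| 0.5 | 37% | 62% | 1.0% |
| 0.7 | 35% | 83% | 0.2% |
| 0.85 | 34% | 98% | about 0% |

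**Step 3, other sizes (unpaired vs paired).**
- n = 10, d = 0.5: 18% vs 17% at rho 0, 12% vs 29% at 0.5, 5% vs 73% at 0.85.
- n = 20, d = 0.8: 71% vs 77% at rho 0.2, 76% vs 92% at 0.5, 86% vs about 100% at 0.85.
- n = 10, d = 1.2: 78% vs 92% at rho 0.5, 85% vs about 100% at 0.85.
- n = 20, d = 1.2: 96% vs 95% at rho 0, 99% vs about 100% at 0.5, about 100% for both at 0.85.

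**Step 4, when is most of the power lost?** Set d so that the paired test has exactly 80% power. Unpaired power is then:

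| rho | n = 5 | n = 10 | n = 20 |
|---|---|---|---|
| 0 | 91% | 85% | 82% |
| 0.3 | 81% | 73% | 70% |
| 0.5 | 69% | 58% | 54% |
| 0.6 | 58% | 47% | 42% |
| 0.7 | 45% | 32% | 27% |
| 0.8 | 28% | 15% | 10% |

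Unpaired power falls below 40%, half of 80%, only when rho exceeds about 0.6 to 0.75, depending on n.

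**The case against.** **The comparisons may be between diagnoses.** Hypothesis H1 and Aim 2b concern differences from controls, and the network analysis compares PPD with controls under each condition. If the qRT-PCR comparisons are PPD versus control at baseline, after E/P and after withdrawal, an unpaired test fits. This stands in part: the text is ambiguous, and the point is limited to contrasts between conditions. It does not remove the point, because the sentence carries no such limit and follows directly on a list of hormone conditions. (Controls are matched, "women with PPD and control women (matched for age, race and parity"), but the plan does not say whether individually; that is a separate matter.)

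**The size is unknown.** A reader might infer that most of the power is discarded. The documents do not support that. At rho 0.2 to 0.3 the loss is about 4 to 10 points (n = 10, 0.8 SD), and at rho 0 the unpaired test is slightly better. Genes sent to validation have already been found differentially expressed, so effects could be large and the loss small. Nor can a high correlation be borrowed from section 10, where "the between-subject standard deviation is 0.69 and the within-subject standard deviation is 0.28". Those values imply 0.69^2/(0.69^2 + 0.28^2) = 0.86, but they describe a clinical outcome, not gene expression.

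**The consequence is not written down.** A reader might infer that genes will be labelled unconfirmed if the t-test is not significant. No such rule appears; qRT-PCR is said only to quantify the genes.

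**The ANOVA already handles the repetition.** It does so for the sequencing data. The validation paragraph does not extend it to qRT-PCR.

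**Conclusion.** The point holds for contrasts between hormone conditions within a line. There the stated test ignores the pairing, conflicts with the plan's own within-groups factor, and is conservative for any positive within-line correlation. Positive correlation is a reasonable expectation, since all conditions of a line share a donor and a derivation, but its size is not given.

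The loss is conditional: at 10 lines and 0.8 SD it runs from none at rho 0, through about 25 points at 0.5, to about 64 points at 0.85. It is negligible at 20 lines and 1.2 SD. All of these rest on assumed line numbers, effects and correlations. The point does not extend to PPD versus control at a single condition, where the unpaired test is suitable, and it does not touch the clinical mood analysis in section 10.

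**What to change.** Replace the sentence on the t-test with text that names the comparisons and the test for each:

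- **Between hormone conditions within a diagnosis:** paired t-test, or the same repeated-measures model as for the sequencing data, with line as the subject.
- **PPD versus control at one condition:** unpaired t-test, as now.
- **Differential hormone response:** unpaired t-test on each line's change between conditions, or the group-by-condition interaction.

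Stating the number of lines would let readers judge the power of this step.

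**Cost.** A sentence or two, with no extra assays or samples. If the within-line correlation is near zero, pairing costs a few points of power: 36% instead of 40% with 10 lines and 0.8 SD. With very few lines the cost is larger because of the lost degrees of freedom: with 5 lines at rho 0, 80% instead of 91%, and about level (80% against 81%) at rho 0.3.
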